2.2 Rationale

The rationale of this study is to determine the delivery rate and the extent of absorption of fentanyl drug release from FDA-approved TDDS products (reference e.g. Duragesic®, versus Mylan transdermal patches) that have different inactive ingredients. can be determined in humans by accurately quantifying residual drug from TDDS post-wear, and the delivery rate can be determined in pharmacokinetic studies. This study will compare fentanyl levels by using in vitro skin flux permeation studies, as a predictor of in-vivo bioequivalence and pharmacokinetics of Duragesic® and Mylan fentanyl TDDS. This will be done through development of an appropriately controlled and well-characterized in-vitro methodology to quantify the in-vivo exposure of healthy adults to fentanyl during TDDS wear, so that the rate of drug delivery can be defined in a manner that can help the regulatory agency (FDA) in developing Guidance for Industry regarding the characterization of drug release and absorption kinetics to ensure the safety of individuals utilizing these types of products.

In the clinical study component, we will employ two types of evaluation to determine the rate and extent of drug release and absorption from fentanyl TDDS, namely residual drug analysis post-wear and pharmacokinetic analysis in healthy adult Subjects. In addition, we will compare the serum drug concentrations following TDDS and intravenous administration, in

order to explore bioequivalence of these TDDSs. We will conduct residual drug analysis of TDDS following in vivo wear using highly sensitive validated quantification methods.

Duragesic® versus Mylan (fentanyl) TDDS

	Duragesic®	Mylan (fentanyl) TDDS
Inactive ingredients	polyester/ethyl vinyl acetate, polyacrylate adhesive	dimethicone NF, polyolefin film backing, silicone adhesive
TDDS type	Matrix	Matrix
Manufacturer	Janssen	Mylan

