6 STUDY PRODUCT

6.1 Study Product Description

6.1.1 Duragesic® (fentanyl) TDDS 25 µg/h

Duragesic® is a prescription TDDS that contains fentanyl which is a federally controlled substance (CII). Duragesic® TDDSs deliver fentanyl at a rate of 25 µg/h and are only for patients with chronic (around the clock) pain that is moderate to severe and expected to last for weeks or longer.

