6.1.2 Mylan (fentanyl) TDDS 25 µg/h

Mylan (fentanyl) is a prescription TDDS that contains fentanyl which is a federally controlled substance (CII). Mylan (fentanyl) TDDS deliver fentanyl at a rate of 25 µg/h and are only for patients with chronic (around the clock) pain that is moderate to severe and expected to last for weeks or longer.

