8.3 Final Analysis Plan

The primary statistical analysis will be performed on the natural log transformed AUC_{0-t} , AUC_{0-A} and C_{max} of Fentanyl from the three Study Sessions using SAS V 9.3. A linear mixed effects model will be used to assess the effects of treatment, Session, sequence and Subject within sequence on natural log transformed AUC_{0-t} , AUC_{0-C} and C_{max} . The treatment, Session, sequence effect will be treated as fixed effects and assessed at a significance level of 0.05. The Subject within sequence will be treated as a random effect. Intra and inter individual variabilities will be obtained. The least square mean estimates for the adjusted differences between treatment means (the log transformed AUC_{0-t} , AUC_{0-C} and C_{max}) and the standard error associated with these differences will be obtained. The geometric means for AUC_{0-a} will be obtained by exponentiating the log transformed AUC_{0-i} for all the three treatments to determine the absolute bioavailability.

The absolute bioavailability for Duragesic® TDDS and Mylan fentanyl TDDS will be calculated.

The analyses for IV administration of fentanyl citrate will be as follows:

Non compartmental and compartmental analyses will be conducted to estimate the PK parameters such as clearance, volume of distribution, elimination rate constant, maximum serum concentration; time of maximum serum concentration and area under the serum concentration-time curve. All analyses will be conducted using Phoenix® WinNonlin® 6.3 (Pharsight, a Certara Company, CA). Absolute bioavailability will be calculated.

The analyses for both TDDS applications (Duragesic® and Mylan fentanyl) will be as follows:

The serum fentanyl concentrations will be determined and the PK parameters such as C_{max} , T_{max} , AUC, steady concentrations (C_{ss}) of fentanyl in each Subject will be elucidated. The rate of fentanyl absorption in each Subject is calculated by dividing the C_{ss} by the clearance predicted from the IV bolus data.

Cumulative amount of fentanyl released by Duragesic® at the end of study Session will be obtained by subtracting residual fentanyl still remaining in the TDDS at the end of the study Session from the total amount of the drug present in an unused TDDS.

Similarly, cumulative amount of the drug released by the Mylan TDDS at the end of study Session is computed.

The rate of drug release from Duragesic® and Mylan TDDS will be determined.

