The means of fentanyl release rates from Duragesic® TDDS, standard deviations from their mean, and 95% confidence intervals will be determined and tabulated. The statistical significance of difference between the means will be evaluated by two-tailed Student's t-test.

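### Section 8.3 divides Css by IV clearance to get each subject's fentanyl absorption rate; the rate is Css multiplied by clearance

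*Combined protocol and SAP*

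**What the plan says.** Section 8.3 plans to estimate clearance from the intravenous session and a steady serum concentration (Css) from each patch application. It then combines them: each subject's absorption rate is "calculated by dividing the C_{ss} by the clearance predicted from the IV bolus data".

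This is the only formula for a PK-derived absorption rate in the text available for this review. It serves a stated purpose, since section 2.2 holds that "the delivery rate can be determined in pharmacokinetic studies". The natural benchmark is the labelled rate, which is the same for both products. Section 6.1.1 states that "Duragesic® TDDSs deliver fentanyl at a rate of 25 µg/h", and section 6.1.2 that "Mylan (fentanyl) TDDS deliver fentanyl at a rate of 25 µg/h".

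Section 8.3 goes on to the residual-drug calculation, which uses neither Css nor clearance, and adds: "The rate of drug release from Duragesic® and Mylan TDDS will be determined". It ends with summary statistics, "The means of fentanyl release rates from Duragesic® TDDS, standard deviations from their mean, and 95% confidence intervals will be determined and tabulated", and a test, "The statistical significance of difference between the means will be evaluated by two-tailed Student's t-test". It does not say whether those release rates are the residual-drug rates only or also include the Css-derived rate.

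**The concern.** The steady-state relation between input rate, concentration and clearance is Css = R/CL. Recovering R therefore means multiplying Css by CL. Section 8.3 divides instead. The operation is written out in words, so this is not a symbol lost when the text was extracted.

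If the sentence is executed literally, the per-subject results are not rates. They cannot be set against the nominal 25 µg/h or against a rate from residual drug. Subjects who absorb equally but clear fentanyl at different speeds would appear to differ. The summary statistics and the t-test would be affected only if the release rates named there include this quantity.

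**Working it through.** **Inputs.** The formula is from section 8.3. The nominal rate of 25 µg/h is from sections 6.1.1 and 6.1.2. The documents give no clearance or Css values, so the clearances of 30, 45 and 60 L/h are assumptions for illustration. The plan reports no numerical result from this formula, so there is no figure to reproduce.

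**1. Units.**
- As written: Css / CL = (µg/L) / (L/h) = µg·h/L².
- Multiplied: Css × CL = (µg/L) × (L/h) = µg/h.

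Only the second is mass per time.

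**2. Mass balance.** At steady state R = Css × CL, so Css = R/CL. Substituting into the written formula gives Css/CL = R/CL². The divisor is the square of clearance. With individual clearances it differs from subject to subject, and no single conversion factor repairs it.

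**3. Worked values for a true rate of 25 µg/h.**

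| Assumed CL (L/h) | Css = 25/CL (µg/L) | Css / CL, as written (µg·h/L²) | Css × CL (µg/h) |
|---|---|---|---|
| 30 | 0.833 | 0.0278 | 25 |
| 45 | 0.556 | 0.0123 | 25 |
| 60 | 0.417 | 0.0069 | 25 |

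**4. Spurious differences between subjects.** At equal R, the apparent ratio is the squared ratio of clearances: 1.5² = 2.25 and 2² = 4. This does not depend on the units or on the assumed values.

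**5. Reversed order.** Take two subjects with the same Css of 0.6 µg/L and clearances of 30 and 60 L/h.
- True rates: 0.6 × 30 = 18 and 0.6 × 60 = 36 µg/h.
- Written formula: 0.6/30 = 0.020 and 0.6/60 = 0.010.

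The subject with the higher absorption rate gets the lower value.

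**6. What is not affected.** Within one subject clearance cancels. For true rates of 20 µg/h on one patch and 25 µg/h on the other, (20/CL²)/(25/CL²) = 20/25 = 0.80 at any CL, the same as with the correct formula. The primary AUC0-t and Cmax analysis, AUC-based absolute bioavailability and the residual-drug amounts do not use this formula at all.

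**The case against.** The strongest reply is that this is a slip of wording with a short reach. A pharmacokineticist would multiply by habit, and results near 0.01 would not pass for 25 µg/h. The plan attaches no explicit threshold or decision to the quantity. All of that is fair, and it limits the seriousness. But section 8.3 is the prespecified analysis, and an analyst who multiplied would be departing from it.

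A second reply concerns the last lines of section 8.3. The plan uses absorption for the Css-derived quantity and release for the residual-drug quantity, so the tabulated release rates and the t-test are most naturally read as residual-based. No effect on them can be shown.

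Third, the plan does not say outright whether the clearance is individual or pooled. With a pooled value, Css/CL and Css × CL differ by one constant, CL². Two subjects with equal absorption and a 2-fold difference in true clearance would then appear 2-fold apart under either formula. The 2.25-fold and 4-fold figures therefore assume individual clearance. That is the likelier reading, since the sentence speaks of each subject's rate and section 4 makes every subject his or her own control. The units are wrong on either reading.

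Finally, multiplication returns 25 µg/h exactly only at true steady state. Section 4 puts the half-life at about 24 hours, so 72 hours of wear is 72/24 = 3 half-lives. A one-compartment model with constant input would then reach 1 − 2⁻³ = 87.5% of steady state, giving 0.875 × 25 ≈ 21.9 µg/h if the 72-hour concentration were taken as Css. This limits Css itself and does not make division right.

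**Conclusion.** The concern holds: the formula is wrong as written, and nothing in the text reviewed corrects it. The conclusion rests only on units and steady-state mass balance, not on the assumed clearances.

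The error should be fixed, but it does not threaten the trial's main comparison. It invalidates one planned output, the absolute PK-derived absorption rate in each subject. The size, R/CL² in place of R, assumes that each subject's own clearance is used. Any effect on the tabulated release rates and the t-test depends on those rates including the PK-derived quantity, which the plan leaves unstated.

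**What to change.** In section 8.3, replace the sentence with: absorption rate (µg/h) = Css (µg/L) × CL (L/h), using the subject's own Session I clearance. Giving the units makes the same slip easy to catch, and naming the clearance removes the individual-or-pooled ambiguity. If a document not reviewed here, such as the Manual of Procedures, already has the correct formula, the two should be reconciled.

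The cost is one corrected sentence. Css and IV clearance are already planned, so no new samples, visits or analyses are needed. While the section is open, a clause could say whether the tabulated release rates are residual-based, PK-based or both, but the correction does not depend on it.

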Session I of an intravenous fentanyl citrate administration, with at least a one week washout interval between Study Sessions.

The study products are:

- Single intravenous (100 µg) administration of fentanyl citrate (50 µg/mL)
- Duragesic® TDDS containing fentanyl (25 µg/h) to be worn for 3 days (72h)
- Mylan fentanyl TDDS (Generic) containing fentanyl (25 µg/h) to be worn for 3 days (72h)

Each Subject will be his/her own control.

Administration of naloxone injection will be used to test for withdrawal prior to using any study products, and to be used emergently in case of fentanyl toxicity. Naltrexone oral tablets will be used to block the opioid receptors to avoid any clinical effects or side-effects of fentanyl.

Blood samples will be obtained as follows (based on administration route):

- 60 min pre-IV administration and then up to 36 hr (1.5 days) post start of IV administration
- 60 min pre-application and then up to 192 hr (8 days), during 3 day wear and post removal of RLD
- 60 min pre-application and then up to 192 hr (8 days), during 3 day wear and post removal of Generic product

B) Residual Drug Analysis determination of Strength

In conjunction with the above described study residual drug analysis will also be conducted for the used RLD and Generic TDDS described in Part A.

- Prior to administration to the Subject as described in Part A, the TDDS will be weighed and the weight recorded.
- The pouch, release liner and all items coming into contact with the TDDS (gloves, forceps, etc.) to be applied in Part A will be retained for analysis.
- The used TDDS will be retained for drug content analysis.
- Upon removal of the product after prescribed wear Session, the skin (at site of application) will be swabbed and the swab retained for drug content analysis.
- All items coming into contact with the TDDS during removal from the Subject and storage in a separate labeled sealable foil pouch for analytical retention will be analyzed for drug content.

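### Section 8.3 calculates released fentanyl with no term for the off-patch drug collected in Part B, so drug on removal and storage items reads as released; the treatment of application items and the skin swab is left open

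*Combined protocol and SAP*

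**What the plan says.** Section 8.3 gives a two-term rule for Duragesic: "subtracting residual fentanyl still remaining in the TDDS at the end of the study Session from the total amount of the drug present"; the starting amount is that of an unused patch. It carries the rule over to the generic: "Similarly, cumulative amount of the drug released by the Mylan TDDS at the end of study Session is computed". Release rates follow, and their means are compared by a two-tailed t-test.

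Part B of the Protocol Summary collects more than the worn patch:

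- Application side: "The pouch, release liner and all items coming into contact with the TDDS", with gloves and forceps as examples, "to be applied in Part A will be retained for analysis".
- Skin surface: after wear, "the skin (at site of application) will be swabbed and the swab retained for drug content analysis".
- Removal and storage side: "All items coming into contact with the TDDS during removal from the Subject" and its "storage in a separate labeled sealable foil pouch for analytical retention will be analyzed for drug content".

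Section 3.2 says that residual content will serve to estimate how much fentanyl was absorbed from each product, but gives no formula. Section 8.3 does not say how the content of an unused patch is obtained.

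**The concern.** Drug that moves from the patch to a glove, forceps or storage pouch at removal has not been delivered to the subject, yet it is missing from the worn patch. A subtraction that looks only at the worn patch counts it as released. The protocol plans to collect what is needed to correct this, but the analysis section does not use it.

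Release rate by product is an objective in Section 3.1, and the rationale in Section 2.2 leans on accurate residual quantification. An upward bias in released amount would pass into the release rates, and into the absorbed amount if the same figure is reused. Without a written rule, the choice of which recovered amounts to subtract could also be made after the assays are seen.

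**Working it through.** The plan states no figure to reproduce, so the check is a mass balance followed by an illustration of scale.

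**Inputs.** From the Protocol Summary: nominal rate 25 µg/h, wear time 72 h. The documents give no value for any of the following:

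- C: content of an unused patch
- R: residual in the worn patch
- A: drug on pouch, liner and application items
- V: drug on removal and storage items
- S: drug on the skin swab
- B: drug absorbed

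**Step 1, the plan's rule.** Released = C − R.

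**Step 2, where the drug goes.** The total T in the sealed system ends up as T = R + A + V + S + B.

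- If C is measured before opening and handling, C = T and C − R = B + S + V + A.
- If C is measured on patches opened, peeled and handled in the same way, C = T − A and C − R = B + S + V.

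Taking swab drug as having left the patch, the true released amount is B + S. The rule therefore overstates release by V in both cases, and by A as well in the first case only. Neither amount can be negative, so the omission acts only upward.

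**Step 3, absorbed amount.** If C − R is reused as absorbed drug, the overstatement is V + S, plus A in the first case. If part of S is adhesive residue, that part never left the matrix; it then inflates released drug too.

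**Step 4, scale.** Nominal delivery is 25 × 72 = 1800 µg. Let H be the handling-item drug wrongly counted (V, or V + A). The 18 to 90 µg range is an assumption, as is release at 80% or 120% of nominal. Rate is taken as amount divided by 72 h.

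| Assumed H | Share of 1800 µg | Shift in rate | If 1440 µg released | If 2160 µg released |
|---|---|---|---|---|
| 18 µg | 18/1800 = 1% | 18/72 = 0.25 µg/h | 18/1440 = 1.25% | 18/2160 = 0.83% |
| 90 µg | 90/1800 = 5% | 90/72 = 1.25 µg/h | 90/1440 = 6.25% | 90/2160 = 4.2% |

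For the absorbed amount, with S assumed equal to H and 1800 µg truly absorbed, the overstatement is (18 + 18)/1800 = 2% to (90 + 90)/1800 = 10%.

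**Step 5, between products.** The shift in the rate difference is (H for one product − H for the other)/72. Equal amounts give 0. The widest gap within the assumed range gives (90 − 18)/72 = 1.00 µg/h, which is 1.00/25 = 4% of the nominal rate.

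**The case against.** The best reply is that the residual in Section 8.3 may mean the whole Part B result. Drug that reaches a glove during removal was still in the patch when wear ended, and Part B lists removal items and the swab under residual drug analysis. On that reading removal-item drug would be added back. The wording allows this but does not say it, and the natural sense of drug remaining in the patch is narrower.

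A second reply is that the detail may sit elsewhere. Section 7 is not in the text available for this review, nor is the Manual of Procedures that Section 4 cites. The citation there concerns the intravenous infusion, and nothing supplied shows that the Manual covers this calculation, but it may. That is why a cross-reference would be enough.

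Residual content is also not the only route to absorption: Section 8.3 separately derives an absorption rate from serum levels and intravenous clearance, and calculates absolute bioavailability.

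Three stronger readings might be inferred, and the documents do not support them:

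- That drug on application gloves and forceps is always counted as released. It is not if unused patches are handled in the same way before assay. Subtracting it regardless could understate release.
- That the product comparison is biased. A common off-patch amount cancels. Section 2.2 lists different adhesives, but nothing shows that off-patch amounts differ.
- That the comparison of residual amounts in Section 8.1 is distorted. It compares the residuals directly and does not pass through the subtraction.

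**Conclusion.** The gap stands in a limited form. As supplied, Section 8.3 has no term for off-patch drug. On its natural reading it counts drug on removal and storage items as released; the pouch, liner and application items depend on how unused content is measured; the swab matters if the same figure is used for absorption. The direction is upward, provided the unused content is itself accurate.

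The size cannot be determined from the documents and may be small. The figures of 1 to 5%, or 0.25 to 1.25 µg/h, rest wholly on an assumed 18 to 90 µg. The between-product t-test moves only if off-patch amounts differ by product. AUC and Cmax, the primary endpoints in Section 8.2.1, come from serum concentrations and are unaffected. This is a minor clarification outside the primary endpoints.

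**What to change.** In Section 8.3:

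1. State how the content of an unused patch is obtained for each product, and whether it includes drug that would stay on the pouch, liner and application items.
2. Define released = unused content − residual in the worn patch − drug on removal and storage items. Subtract pouch, liner and application-item drug only if the unused content includes it.
3. Define absorbed = released − skin swab, and note that the swab may carry adhesive residue, so its drug may not all have left the matrix.
4. Report recovered amounts by item type and product, so that readers can see whether they matter and whether they differ.

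If Section 7 or the Manual of Procedures already defines this, a cross-reference is enough.

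The cost is analysis-plan wording, using samples that the protocol already collects. Part B commits to analyzing the removal items, but says only that the pouch, liner and application items are kept for analysis, so confirm that they are assayed. The downside is slight added assay noise from low recovered amounts and a slightly lower reported release.

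### Section 8.3 measures released fentanyl against an unused-patch content of unstated source, and the error in that reference is left out of the SD, 95% CI and t-test for release rate

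*Combined protocol and SAP*

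**What the plan says.** Section 8.3 (Final Analysis Plan) defines the cumulative amount released by Duragesic as follows: "subtracting residual fentanyl still remaining in the TDDS at the end of the study Session from the total amount of the drug present in an" (the sentence then names an unused patch). For the generic it adds: "Similarly, cumulative amount of the drug released by the Mylan TDDS at the end of study Session is computed". So each product has its own reference content. The plan does not state where that content comes from, the lot, the number of unused patches, or how they are assayed.

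The residual, by contrast, is specific to the patch worn. Part B of the Protocol Summary states: "The used TDDS will be retained for drug content analysis". Part B also requires that before application "the TDDS will be weighed and the weight recorded". Section 8.3 gives that weight no role.

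The last paragraph of section 8.3 plans means, standard deviations and 95% confidence intervals for release rate, and then: "The statistical significance of difference between the means will be evaluated by two-tailed Student's t-test". It does not say whether the test is paired, and none of these summaries has a term for uncertainty in the reference content.

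**The concern.** Released amount is reference content minus residual. If the reference for one product is wrong by some amount, every subject's release on that product is wrong by the same amount and in the same direction. The product mean moves while the spread between subjects does not. The SD, the CI and the t-test are all built from that spread, so they treat the reference error as zero. Enrolling more subjects would not help.

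Two things depend on this: the release-rate comparison, which is one of the three objectives in section 3.1, and the estimate of total absorbed fentanyl in section 3.2. A reference error could create an apparent difference between Duragesic and Mylan, or hide a real one, and the reported precision would give no warning.

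**Working it through.** The plan gives no patch content, content tolerance, number of reference units or release SD. There is no planned figure to reproduce, and the sizes below rest on assumptions.

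**Inputs from the documents.** 24 subjects, each wearing both patches; nominal rate 25 µg/h for 72 h, so nominal delivery is 25 × 72 = 1,800 µg; two-sided t-test. The 0.05 level is stated for the mixed model and is assumed here for the t-test.

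**Assumed.** Patch content 2–5 mg (it must exceed 1.8 mg); unit content CV 2–5%; SD of the within-subject difference in release rate 3–8 µg/h; paired test.

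**Step 1. Bias.** Let C_D and C_M be the true mean contents and e_D and e_M the relative errors of the two references. The bias in mean amount released is e × C for each product. The bias in the Duragesic–Mylan difference is e_D·C_D − e_M·C_M, which does not contain n. With both contents at 3,000 µg:
- errors of +5% and 0% give 150 µg, which is 150/1,800 = 8.3% of nominal, or 150/72 = 2.08 µg/h;
- errors of +5% and −5% give 300 µg (16.7%);
- errors of +5% and +5% cancel to 0.

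With unequal contents of 4,000 and 2,500 µg, errors of +5% and +5% leave 200 − 125 = 75 µg (4.2%).

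**Step 2. Sampling error of the reference, as a rate.** With one unit per product, the SD of the shared error is τ = CV × content / 72. For 3 mg and 3%, τ = 0.03 × 3,000/72 = 1.25 µg/h. The variance shared by the product difference is 2τ² = 3.125, or 3.125/m if m units are averaged.

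**Step 3. False-positive rate.** With no true difference, the paired t statistic is inflated by √(1 + r), where r = 24 × (2τ²/m) / V and V is the variance of the within-subject differences. The true rate is the two-sided tail of t on 23 df beyond 2.069/√(1 + r).

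| Central case | V | r | 2.069/√(1 + r) | Rate |
|---|---|---|---|---|
| m = 1, SD 5 includes content variation | 25 | 3.00 | 1.034 | 31% |
| m = 1, SD 5 before content variation | 28.125 | 2.67 | 1.080 | 29% |
| m = 10, SD 5 includes content variation | 25 | 0.30 | 1.814 | 8.3% |
| m = 10, SD 5 before content variation | 28.125 | 0.267 | 1.838 | 7.9% |

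**Step 4. Range.** V must contain the worn patches' own content variation, so V = SD² + 2τ², with SD taken before content variation.
- Mildest corner (2 mg, 2%, SD 8): 7.5% with one unit, 5.2% with ten.
- Harshest corner (5 mg, 5%, SD 3): τ = 3.47, 2τ² = 24.1, V = 33.1. The rate is 63% with one unit and 22% with ten.
- Ceiling: because V cannot be below 2τ², r cannot exceed 24/m. The rate therefore cannot exceed about 68% with one unit or 27% with ten.

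**Step 5. Unit-to-unit variation around a correct reference.** This is noise and is already in the observed SD. With a release CV of 30% (SD 0.3 × 1,800 = 540 µg) and 3 mg patches at 5% CV, the SD becomes √(540² + 150²) = 560 µg, a rise of 3.8%. Over 2–5 mg and 2–5% the rise is 0.3–10%.

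**The case against.** The plan does not say that a single unused patch is used. The same sentence refers to the worn patch in the singular although there are 24 per product, so the singular is generic and a mean of several units is not excluded. This stands, and the one-unit figures show only one end of the possibilities.

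A worn patch cannot be assayed before wear without destroying it, so some unused-patch reference is unavoidable. That also stands. The fault is an unspecified reference treated as known without error, not the use of a reference.

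A reader might infer that all residual-drug work is compromised. The documents do not support that. Residual content is assayed directly on the worn patch, and the comparison of residual amounts in section 8.1 needs no starting content. AUC and Cmax, the primary endpoints in section 8.2.1, are untouched, and section 8.3 plans a separate absorption-rate estimate from serum data.

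A reader might also infer that differences in content between patches bias the comparison, or that the weights are never used. The first is noise (Step 5). The second is shown only for section 8.3: the Manual of Procedures cited in section 4 is not available here, and it may specify lot, replicates or weight normalisation. Such a procedure could make the reference better, but section 8.3 would still summarise and test release rate with no term for the reference's uncertainty.

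**Conclusion.** The point holds in a limited form. As written, section 8.3 leaves a product-wide error out of the precision of the derived amount and rate of release. The reported error bars for each product and for the product difference are too narrow on any reading of the reference, unless its error happens to be negligible.

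The size cannot be derived from the documents. Under the assumed central case, the nominal 5% paired test has a false-positive rate of about 29–31% with one reference unit per product and about 8% with ten. Over the assumed ranges it is about 7–63% with one and 5–22% with ten. These figures cover sampling error of independently assayed references only; a label claim or an assay bias would act as the fixed shift in Step 1. It would be too strong to say that the Duragesic–Mylan difference is known to be biased: its bias is the net of two errors, which may partly or wholly cancel, although nothing in the documents ensures that they do.

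Because a stated objective is affected but no primary endpoint is, this should be corrected but does not threaten the main analysis.

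**What to change.** In section 8.3:

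1. For each product, define starting content as the assayed mean of several unused patches from the same lot as the worn patches, and state the lot, the number of patches and the assay.
2. Weigh those unused patches. If weight predicts content among them, scale the starting content by each worn patch's recorded pre-application weight; otherwise use the lot mean.
3. Add the variance of that reference mean, or of the calibration, to the SE, CI and test for each release rate and for the product difference.

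The cost is a change of wording and a few more assays with the existing method; no subjects or visits are added. Confidence intervals for release will be slightly wider. A systematic bias in the assay itself would not be removed.
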